#### 8.2.3. Sensitivity Analyses of the Primary Analysis

Sensitivity analyses of the primary efficacy endpoint will be conducted to evaluate the robustness of study results under different assumptions and imputation algorithms. For the primary endpoint categorized as absolute SALT score  $\leq 20$  at Week 24, the following sensitivity analyses will be performed for the Efficacy Population only.

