#### 5. ANALYSIS SAMPLES

The Efficacy Population will include all patients who are randomized in the study and dispensed study drug during the Treatment Period and were not treated at site 102. It was determined by the Sponsor during the course of the study that site 102 would be early terminated due to continued failure to comply with study procedures. The decision to exclude subjects treated at site 102 was made prior to unblinding.

The Modified Efficacy Population will include all patients who are randomized in the study and dispensed study drug during the Treatment Period. This population will include subjects from site 102 and will be used for sensitivity analyses of the primary and key secondary endpoints.

The Pharmacokinetic Population will include all patients who receive study drug and have at least 1 pharmacokinetic sample taken during the Treatment Period. Patients who receive placebo will be excluded from the Pharmacokinetic Population.

The Safety Population will include all patients who receive study drug during the Treatment Period. The Safety Population will include patients from site 102.

The Per Protocol Population will include all patients in the Efficacy Population who were dosed according to protocol and have no major protocol deviations. Further details on the identification of major protocol deviations are provided in Section 7.1.

In the event patients incorrectly receive treatment associated with a different treatment group, they will be analyzed "as randomized" for efficacy and "as treated" for safety if the patient received that treatment for more than 50% of doses.

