#### 8.1.4. Multiple Comparisons/Multiplicity

Hierarchical testing will be used to control for multiple comparisons (Figure 1). For the primary efficacy analysis and the key secondary efficacy analyses, a  $\leq 0.025$  (two-sided) alpha-level will be allocated to each dose for comparison with placebo to adjust for multiplicity of testing associated with two doses. Once p>0.025 is observed for a treatment group comparison, inference for additional endpoints is no longer alpha-level protected for that dose group, however nominal p-values will still be reported.

Subsequently, conditional upon significance ( $\leq 0.025$ ) for the primary endpoint and first key secondary endpoint for each dose, a linear hierarchical testing approach with  $\leq 0.025$  (two-sided) alpha-level will be used to test the remaining key secondary endpoint comparisons versus placebo. Once p>0.025 is observed for a treatment group comparison, inference for additional endpoints is no longer alpha-level protected for that dose group; however, nominal p-values will still be reported.

All other statistical tests outside of the hierarchy will be carried out at a two-sided significance level of  $\leq 0.05$ . Nominal p-values will be presented without adjustment for multiple comparisons.

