#### **Figure 1: Hierarchical Testing**

#### 8.3.1. Satisfaction of Hair Patient Reported Outcome (SPRO) at Week 24

The first key secondary endpoint is the percentage of responders per the SPRO at Week 24. The SPRO is a single item questionnaire answered by the patient, designed to measure how satisfied alopecia areata patients are with their hair at the time of the assessment. The SPRO responses are on a scale of 1-5, where 1 = very satisfied, 2 = satisfied, 3 = neither satisfied nor dissatisfied, 4 = dissatisfied, and 5 = very dissatisfied. An example of the SPRO assessment can be found in Appendix 17.4.1 of the protocol.

A responder is defined as patients with answers of "very satisfied" or "satisfied" at Week 24 on the SPRO. This endpoint will be assessed similar to the primary analysis of the primary endpoint, according to Section 8.2.2.

Missing data will be imputed similarly to the primary endpoint according to Section 8.2.1. However, since the SPRO scale is ordinal, the FCS logistic regression method will be used in lieu of the FCS regression method. The missing SPRO scores will be imputed in a sequential manner using logistic regression models with baseline SALT score, baseline SPRO score, and the observed or imputed SPRO values of previous visits as covariates.

The observed number and percentage of SPRO responders by treatment group will be reported along with the appropriate p-values. Both CTP-543 doses will be tested in parallel against placebo with a  $\leq 0.025$  alpha level. This analysis will be completed for the Efficacy Population, the Per Protocol Population, and the Modified Efficacy Population. The Per Protocol Population will be considered supportive. The analysis utilizing the Modified Efficacy Population is considered a sensitivity analysis. If the primary endpoint is unsuccessful, nominal p-values will be reported.

#### 8.3.2. SALT Score ≤ 20 at Weeks 20, 16, 12, and 8

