The next key secondary endpoints are the percentage of patients achieving an absolute SALT score of  $\leq 20$  (i.e., the binary endpoint denoting a SALT score  $\leq 20$ ) at Weeks 20, 16, 12, and 8. Missing data will be imputed according to Section 8.2.1. These endpoints will be assessed according to Section 8.2.2. If the primary endpoint and first key secondary endpoint are unsuccessful, nominal p-values for the SALT key secondary endpoints will be reported. This analysis will be completed for the Efficacy Population, the Per Protocol Population, and the Modified Efficacy Population. The Per Protocol Population will be considered supportive. The analysis utilizing the Modified Efficacy Population is considered a sensitivity analysis.

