  - The SAP adds multiple imputation for the Modified Efficacy Population, which will include site 102. The primary multiple imputation for the Efficacy Population will not include site 102.

- Protocol Section 12.4.5.2 Tipping Point Analyses
  - The protocol states that "The patterns of interest for the tipping point analysis will consider two cases and will estimate tipping points for values where only missing values not at random (MNAR) are adjusted and also where all missing values are adjusted (i.e., two separate tipping point analyses)." The SAP specifies only one tipping point analysis due to the following:
    - This statement assumes that the primary imputation method would employ an MNAR assumption. It was determined that MAR would be reasonable upon blinded review of reasons for missing data, as prespecified in Protocol Section 12.4.4.
    - To test the MAR assumption, an additional sensitivity analysis employing an MNAR assumption was added.
    - The values that will be MNAR for the MNAR sensitivity analysis are study discontinuations due to TEAEs or lack of efficacy. These values will be imputed using the control arm. As such, adjusting these values would shift those patients to be worse than placebo. As placebo in this study is a true placebo, this is not a realistic or informative shift.
  - The protocol states, "Missing values will not be imputed for efficacy endpoints which are not derived from SALT scores." The SAP adds multiple imputation for the SPRO endpoints because SPRO at Week 24 is an alpha-controlled key secondary endpoint and the treatment of missing data should align with the treatment of missing data for the other alpha-controlled endpoints.
- Protocol Section 12.4.8 Safety
  - Adverse Events
    - The protocol states that "Proportions for adverse events that are gender-specific (e.g., dysmenorrhea) will be based on the number of patients from that gender." The SAP specifies that the proportion of adverse events will be based on the number of patients in the safety population, even gender-specific adverse events. This change is in line with previous studies in this program and generally accepted conventions.
  - Clinical Laboratory
    - Two additional presentations of labs were added to the SAP in light of outliers seen in blinded data review throughout the study (IQR) and to observe values over time (by visit summaries).
- Other changes:
  - Analyses for COVID-19 were added in Section 11 of the SAP.

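### The missing-at-random assumption is tested for the primary endpoint only; the key secondaries have no such check, and the SPRO imputation model ignores early SALT scores

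*SAP*

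**What the plan says.** SAP 8.2.3 sets its own scope: "Sensitivity analyses of the primary efficacy endpoint will be conducted to evaluate the robustness of study results under different assumptions and imputation algorithms". Sensitivity 1 (control-arm imputation for selected study exits) and Sensitivity 2 (tipping point) both concern SALT ≤20 at Week 24. Sensitivity 3 changes the population.

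For SPRO at Week 24, SAP 8.3.1 says: "This endpoint will be assessed similar to the primary analysis of the primary endpoint, according to Section 8.2.2". Imputation follows SAP 8.2.1, which is within treatment arm under MAR, but uses "logistic regression models with baseline SALT score, baseline SPRO score, and the observed or imputed SPRO values of previous visits as covariates". For the earlier SALT visits, SAP 8.3.2 says: "Missing data will be imputed according to Section 8.2.1". Each of these endpoints is also run in the Per Protocol Population (supportive) and in the Modified Efficacy Population. SAP 5 says the latter "will be used for sensitivity analyses of the primary and key secondary endpoints".

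SAP 8.1.4 makes the rest of each dose's sequence conditional on significance: "for the primary endpoint and first key secondary endpoint for each dose, a linear hierarchical testing approach" then covers the remaining key secondaries.

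The protocol planned no SPRO imputation. SAP 13 adds it because "the treatment of missing data should align with the treatment of missing data for the other alpha-controlled endpoints". The same section says of the primary endpoint: "To test the MAR assumption, an additional sensitivity analysis employing an MNAR assumption was added". The blinded classification of missing data in SAP 8.2.1 and Protocol 12.4.4 is written for SALT scores.

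**The concern.** SPRO at Week 24 opens the rest of the hierarchy for each dose. Under this SAP its result depends on imputation, and no planned analysis shows how far it depends on MAR. The protocol's estimand (Protocol 12.4.2) is response at Week 24 whether or not treatment continued. Own-arm imputation may credit a patient who stopped drug with the response of patients who mostly stayed on it.

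SPRO has a second weakness, which is separate from any departure from MAR. Its imputation model leaves out information the trial collects, namely SALT at Weeks 4 and 8. If patients with little early regrowth tend to leave, the SALT imputation can use that fact and the SPRO imputation cannot. At stake are the SPRO claim and the earlier-week SALT claims, mainly at 8 mg.

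**Working it through.** **1. The plan's own figure.** The protocol gives power for the primary endpoint only (Protocol 12.1): 40%, 26% and 9% with 110, 220 and 110 patients, two-sided alpha 0.025, continuity-corrected. For 8 mg:
- Pooled rate (110×0.09 + 220×0.26)/330 = 0.2033; null SE 0.0470; alternative SE 0.0402; correction 0.5×(1/110 + 1/220) = 0.0068.
- (0.17 − 0.0068 − 2.2414×0.0470)/0.0402 ≈ 1.44, so power is 92.5% (stated: about 92%). For 12 mg it is 99.9% (stated: >99%).

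The documents give no power, SPRO rate or missingness rate for the key secondaries. **Every input below is therefore an assumption.**

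**2. Coverage by endpoint.**

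| Endpoint | Base imputation | Departure from MAR tested? | Blinded review of reasons? |
|---|---|---|---|
| SALT ≤20, Week 24 | MAR, own arm | Yes: Sensitivity 1 and 2 | Yes |
| SPRO, Week 24 | MAR, own arm | No | Not named |
| SALT ≤20, Weeks 20, 16, 12, 8 | MAR, own arm | No | Yes (missing SALT, by visit) |

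**3. What the SPRO model knows about a patient who leaves after Week 8.** SPRO is scheduled at Baseline and Weeks 12, 16, 20 and 24 (Protocol Table 2 and footnote 12). SALT is scheduled from Week 4. The leaver's SPRO is imputed from arm, baseline SALT and baseline SPRO. An early termination visit does not help: SAP 8.1.2 allows reassignment only to visits where the assessment was scheduled, and the Week 12 efficacy window opens on Day 82.

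**4. Control-arm arithmetic.** Let m be the share missing after stopping drug, with placebo-like response afterwards. The difference becomes (1−m)·pT + m·pP − pP = (1−m)(pT − pP). Differences of 10, 20 and 30 points fall by 0.5, 1.0 and 1.5 points at m = 5%, and by 1.0, 2.0 and 3.0 at m = 10%.

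Significance requires d/√(pT(1−pT)/n + pP(1−pP)/110) > 2.2414. For 8 mg with placebo at 10%, the smallest significant d is 8.71 points. To survive m = 10%, the MAR difference must be 8.71/0.9 = 9.68 points, which is a MAR p-value of 0.0136. Over placebo rates of 1–20%, the MAR p-value must be below about 0.019–0.020 (m = 5%) or 0.013–0.016 (m = 10%).

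**5. Chance that a significant MAR result loses significance.** Exact binomial sum over both arms, unstratified, ignoring between-imputation variance.

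| Scenario | MAR power | m = 5% | m = 10% |
|---|---|---|---|
| 8 mg SPRO, 20 vs 10% | 62% | 3.7% | 7.8% |
| 8 mg SPRO, 25 vs 10% | 91% | 1.8% | 4.1% |
| 8 mg SPRO, 35 vs 15% | 97% | 0.8% | 1.9% |
| 8 mg early SALT, 8 vs 2% | 67% | 2.0% | 7.3% |
| 8 mg early SALT, 12 vs 3% | 84% | 2.0% | 4.4% |
| 12 mg SPRO, 36 vs 10% | – | 0.16% | 0.46% |
| 12 mg SPRO, 52 vs 19% | – | 0.05% | 0.13% |

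**6. Simulation of the SPRO model.** Week 24 SALT response was set to 40/26/9%. SPRO was a latent score driven by SALT plus patient and visit error. Two sets of cut-points gave SPRO response of about 36/25/10% and 52/39/19%. Loss was equal across arms and all leavers left after Week 8, the worst case for this model. Bias in the difference from placebo, in points (Monte Carlo SE at most 0.17):

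| Who leaves, and what follows | 12 mg, 5% | 12 mg, 10% | 8 mg, 5% | 8 mg, 10% |
|---|---|---|---|---|
| Poorest Week 8 regrowers, course unchanged | +1.1 to +1.3 | +2.1 to +2.6 | +0.7 to +0.8 | +1.1 to +1.4 |
| Poorest Week 8 regrowers, then placebo-like | +1.2 to +1.5 | +2.3 to +3.1 | +0.7 to +0.9 | +1.2 to +1.7 |
| Random leavers, then placebo-like | +1.1 to +1.5 | +2.5 to +3.2 | +0.7 to +1.0 | +1.4 to +1.9 |

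The first row is a fault of the model's covariates, not of MAR as such: Week 24 SALT bias in that row is 0.0. A separate simplified simulation of the same mechanism gave +1.4 and +2.6 points (12 mg) and +0.9 and +1.6 (8 mg) at 5% and 10%. These fell to about zero once SALT at Weeks 4 and 8 entered the model. The last row is a true departure from own-arm MAR, and better covariates do not cure it.

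**7. Direction.** Take 5% loss on 8 mg, 20% on placebo, no response after leaving, and SPRO 25% vs 10%. The bias is 0.05×25 − 0.20×10 = −0.75 points, against the drug.

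**8. Primary endpoint.** At m = 10% with the treated shift at 100% and the placebo shift at 0, response is 0.9×40 = 36.0% and 0.9×26 = 23.4%. Control-arm imputation adds 0.1×9 = 0.9, giving 36.9% and 24.3%. The tipping-point grid therefore contains a case stricter than control-arm imputation of every missing value.

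**The case against.** **Nothing was dropped.** The protocol's tipping point was also limited to the primary endpoint. The alignment sentence in SAP 13 justifies imputing SPRO, and the SAP does impute it. The sentence about testing MAR explains a change to the primary endpoint's sensitivity analyses. This stands: the plan is incomplete here, not self-contradictory.

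**A crude check may already exist.** SAP 4 makes the population count the default denominator, and SAP 8.3.1 reports observed SPRO responders. Unless a table shell says otherwise, that percentage counts missing patients as non-responders. This stands in part. It carries no interval or p-value of its own, and SAP 8.2.2 refers to non-imputed data, so the SALT display is less clear.

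**Little SPRO may be missing.** Patients who stop drug are followed with all endpoints collected (Protocol 8.3 and 9.2.1), and SPRO can be done by video (Protocol 10.5). This also stands. It cuts the other way too: COVID-19 site closures and travel limits, the SAP's example of plausible MAR, prevent a SALT assessment (Protocol 10.2) but explain missing SPRO less well.

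**A stronger reading about Sensitivity 1.** A reader might infer a hole in the primary analysis, because Sensitivity 1 moves to the control arm only exits whose reason is recorded under withdrawal of consent. The documents do not support that. The tipping point shifts every imputed Week 24 value whatever the exit reason, once the primary result is significant. The eCRF options are not shown. Protocol 8.3 and 9.5 also differ on whether a patient needing prohibited medication leaves treatment or the study, so the number of exits missed cannot be judged.

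**Conclusion.** The point holds and is minor. No departure from MAR is planned for any key secondary. For SPRO the imputation model also omits collected data that bear on who leaves, and the blinded review does not name SPRO.

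With 5–10% missing, all after Week 8, SPRO bias is about +1 to +3 points (12 mg) and +0.7 to +1.9 points (8 mg). The 12 mg figures sit on simulated differences of about 26–33 points. The chance of losing significance is about 1–8% for 8 mg and under 0.5% for 12 mg; the highest SPRO figure needs a scenario with 62% power. Effects are smaller for leavers who already have a Week 12 SPRO, and at visits with less missing data.

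It does not follow that the SPRO result will be inflated: the rates are unknown and the sign can reverse. Nor is the primary conclusion in doubt.

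**What to change.** Before unblinding, by SAP addendum:

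1. **SAP 8.3.1.** Add observed or imputed post-baseline SALT, including Weeks 4 and 8, to the covariates of the SPRO imputation model itself. It belongs in the alpha-controlled analysis, not only in a sensitivity run.
2. **SAP 8.3.1 and 8.3.2.** Add one control-arm sensitivity analysis for SPRO at Week 24 and for SALT ≤20 at Weeks 20, 16, 12 and 8. Any value missing after permanent discontinuation of study treatment is imputed from the placebo arm, unless the blinded review documents a COVID-19 logistics reason. All other missing values stay on own-arm imputation.
3. **SAP 8.2.1.** Extend the blinded review of reasons for missingness to SPRO at Week 24.

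The primary analysis, its existing sensitivity analyses, the testing order and the alpha stay as they are. The cost is modest programming on data already collected, and sensitivity estimates that may be less favourable. If the blind is already broken, leave the planned SPRO analysis unchanged and report items 1 and 2 as post hoc under SAP 8.1.3.

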#### Sensitivity 1: Multiple imputation; missing not at random (MNAR)

This sensitivity analysis is an implementation of a pattern mixture model that draws from different populations based on the reason for withdrawal from study. Patients who discontinued the study early due to a treatment-emergent adverse event (including COVID-19) or due to lack of efficacy will be considered MNAR. Treatment-emergent adverse event and lack of efficacy are reasons collected under "If 'Withdrew Consent', specify reason" on the *Study Discontinuation/Completion* eCRF page.

For patients who discontinued the study early due to a treatment-emergent adverse event or lack of efficacy, SALT scores missing after discontinuation will be imputed using the control arm. This assumes that patients, regardless of treatment, who discontinue the study early for those reasons would have similar SALT scores to placebo patients with complete data.

For patients who discontinued the study due to reasons other than treatment-emergent adverse event or lack of efficacy, missing SALT scores after subjects discontinue the study early will be multiply imputed from subjects within the same treatment group who have complete data at that time. Terms will include baseline values and the weekly data through the time point being imputed.

The proportion of patients who have a SALT score  $\leq 20$  will be calculated for each imputed dataset. The primary analysis, as described in Section 8.2.2, will be repeated for the Efficacy Population using the MI with MNAR assumption datasets.

#### Sensitivity 2: Tipping point

Additionally, a tipping point analysis will be conducted for each dose compared to placebo at Week 24 if the result of the MI analysis is statistically significant at the alpha  $\leq 0.025$  level, in favor of treatment, for the given dose. The tipping point analysis will use the primary MAR assumption datasets, where all imputed values are adjusted.

The tipping point analysis will apply delta adjustments for both treated and placebo. For the tipping point analyses,  $\delta T$  values (adjustments for treated patients) will represent a percentage difference between the imputed value and baseline and can vary from 0% to 100% of the difference for subjects with an imputed SALT score less than baseline, or zero otherwise. For the placebo arm,  $\delta P$  values will represent a percentage difference between the imputed value and 0 hair loss. Accordingly, the maximum delta value of 100% provides for an adjusted imputed value equal to either baseline (for treated subjects, representing non-response) or zero hair loss for placebo, representing response. Tipping points will therefore be provided for combinations of  $\delta T$  and  $\delta P$  to provide a range of assumptions about hypothetical improvements on placebo missing data values and reduction in efficacy for treated imputed values such that there is no longer evidence of efficacy.

#### **Sensitivity 3: Modified Efficacy Population**

A third sensitivity analysis will be done utilizing the Modified Efficacy Population. The primary analysis will be repeated, as described in Section 8.2.2.

#### 8.2.4. Secondary Analyses of the Primary Endpoint

No secondary analyses specified.

#### 8.3. Key Secondary Endpoints

The below figure displays the order of testing of the key secondary endpoints. See also Section 8.1.4.

#### **Figure 1: Hierarchical Testing**

#### 8.3.1. Satisfaction of Hair Patient Reported Outcome (SPRO) at Week 24

The first key secondary endpoint is the percentage of responders per the SPRO at Week 24. The SPRO is a single item questionnaire answered by the patient, designed to measure how satisfied alopecia areata patients are with their hair at the time of the assessment. The SPRO responses are on a scale of 1-5, where 1 = very satisfied, 2 = satisfied, 3 = neither satisfied nor dissatisfied, 4 = dissatisfied, and 5 = very dissatisfied. An example of the SPRO assessment can be found in Appendix 17.4.1 of the protocol.

A responder is defined as patients with answers of "very satisfied" or "satisfied" at Week 24 on the SPRO. This endpoint will be assessed similar to the primary analysis of the primary endpoint, according to Section 8.2.2.

Missing data will be imputed similarly to the primary endpoint according to Section 8.2.1. However, since the SPRO scale is ordinal, the FCS logistic regression method will be used in lieu of the FCS regression method. The missing SPRO scores will be imputed in a sequential manner using logistic regression models with baseline SALT score, baseline SPRO score, and the observed or imputed SPRO values of previous visits as covariates.

The observed number and percentage of SPRO responders by treatment group will be reported along with the appropriate p-values. Both CTP-543 doses will be tested in parallel against placebo with a  $\leq 0.025$  alpha level. This analysis will be completed for the Efficacy Population, the Per Protocol Population, and the Modified Efficacy Population. The Per Protocol Population will be considered supportive. The analysis utilizing the Modified Efficacy Population is considered a sensitivity analysis. If the primary endpoint is unsuccessful, nominal p-values will be reported.

#### 8.3.2. SALT Score ≤ 20 at Weeks 20, 16, 12, and 8

The next key secondary endpoints are the percentage of patients achieving an absolute SALT score of  $\leq 20$  (i.e., the binary endpoint denoting a SALT score  $\leq 20$ ) at Weeks 20, 16, 12, and 8. Missing data will be imputed according to Section 8.2.1. These endpoints will be assessed according to Section 8.2.2. If the primary endpoint and first key secondary endpoint are unsuccessful, nominal p-values for the SALT key secondary endpoints will be reported. This analysis will be completed for the Efficacy Population, the Per Protocol Population, and the Modified Efficacy Population. The Per Protocol Population will be considered supportive. The analysis utilizing the Modified Efficacy Population is considered a sensitivity analysis.

